7.10 Changes to Planned Analysis

7.10.1 Vaginal pH endpoint

Vaginal pH was not defined in the CIP as an endpoint. This was added as an exploratory endpoint that will be analysed as described in Section 7.9.5. In addition, an objective for this endpoint was added.

7.10.2 Clarification on exploratory endpoint regarding correlation of fungus and clinical cure

The CIP stated as exploratory endpoint:

“Correlation of presence of fungus as analysed by vaginal swab DNA-analysis on Days 0, 7, 14 and 25 and presence of fungus as assessed by culture, and clinical cure.”

This endpoint has been separated to three endpoints in Section 7.9.5 to clarify the different correlations to be investigated.

7.10.3 Subgroup analyses have been added

Two subgroup analyses have been added summarising the primary endpoint by site and number of previous infections respectively. The idea being to capture any potential treatment heterogeneity upon stratification on these variables.

7.10.4 Day 25 per protocol analysis set

A new analysis population, PPAS25, has been added to be used for efficacy assessments at Day 25. The idea being to take into account protocol deviations affecting Day 25 efficacy analyses specifically (which is not covered explicitly by PPAS).

7.10.5 The section of exploratory endpoints have been elaborated on

New analyses compared to the CSP have been proposed, for example correlation analyses using the magnitude and not only the presence of fungus (see section 7.9.5 above).

8 Derived Variables

8.1 Disposition of Subjects

A screening failure is defined as a patient with a screening visit (Day 0) but answering 'No' to the question 'Is the patient continuing in the study' at the screening visit.

8.2 Change from Baseline

Change from baseline will be computed as the difference between a post-baseline value and the corresponding baseline value.

Percentage change from baseline will be computed as 100 times the change from baseline divided by the baseline value.

8.3 Compliance

Two separate calculations will be used to derive compliance (%).

Patient reported compliance will be calculated as $100 \times$ the number of ordinary study days (0 to 5) the patient responded yes to the question 'Did you apply the pessary' divided by 6.

Statistical Analysis Plan

Study ID: CL4

Pessary kit derived compliance will be calculated as $100 \times 6 \times (\text{number of pessary kit returned} - \text{number of pessaries lost} - \text{number of returned unused pessaries})$ to the clinic divided by 6. Note that this definition implies non-compliance in case of failure to bring back kits to the clinic.

Total study compliance will subsequently be derived as the maximum of patient reported compliance and pessary kit compliance.

References

- [1] ICH Harmonised Tripartite Guideline for Statistical Principles for Clinical Trials E9. February 1998.
- [2] ICH Harmonised Tripartite Guideline for Structure and Content of Clinical Trial Reports E3. November 1995.

Statistical Analysis Plan

Study ID: CL4

9 Signoff

We have read this SAP for the CL4 study and confirm that, to the best of our knowledge, the statistical analyses to be performed in this study are accurately described.

Gedea Biotech AB: *NAME*

SIGNATURE AND DATE

DocuSigned by:

NAME

Signing Time: 25-mar-2024 | 18:30 CET

C021A0A7C87E410FBDBF942B730DA13A

CTC SAP Author / Approver: *NAME*

SIGNATURE AND DATE

DocuSigned by:

NAME

Signing Time: 25-mar-2024 | 18:28 CET

A1F9A57C0B42488887FD67733546F97B

Certifikat om färdigställande

Kuvert-ID: 5B2C2F63C7CE46AA99443AA0722A11DA

Status: Färdigställda

Ämne: Complete with DocuSign: Statistical Analysis Plan, GED004 CL4 FINAL v2.0 25MAR2024.docx

Källkuvert:

Dokumentsidor: 21

Signaturer: 2

Kuvertskapare:

Certifikatsidor: 5

Initialer: 0

NAME

AutoNav: Aktiverat

[name]

Kuverterad stämppling: Inaktiverat

37

Tidszon: (UTC+01:00) Amsterdam, Berlin, Bern, Rome, Stockholm, Vienna

NAME

IP-adress:

Spela in spårning

Status: Original

Hållare: NAME

Plats: DocuSign

25-mar-2024 | 18:27

Signeringshändelser**Signatur****Tidsstämpel**

NAME

NAME

Skickade: 25-mar-2024 | 18:28

Clinical Trial Consultants, CTC AB

Signaturantagande: Förvald stil

Visade: 25-mar-2024 | 18:28

Säkerhetsnivå: E-post, Kontoautentisering
(obligatoriskt)

Signatur-ID:

Signerade: 25-mar-2024 | 18:28

-

Med IP-adress:

Med signeringssautentisering via DocuSign-lösenord

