7.2.2 Manufacturing, packaging and labelling of investigational product

Gedea Biotech AB is the responsible manufacturer of the investigational products (Gedea Pessary). Gedea Biotech AB has subcontracted production, packing, labelling and release testing of the clinical investigation material for use in the clinical investigation to Galenica AB (Malmö, Sweden). Batch release is performed by Gedea Biotech AB Quality Assurance Director.

The investigational products will be packed in blister packs containing 6 pessaries packed together with 6 pessary applicators in a cardboard box (Figure 2 and Figure 3). The cardboard box will be labelled with “Gedea Pessary pHyp”, batch number, study number, package number, manufacturing date and expiry date. The label used in the study will be written in the local language.

Labels will be prepared in accordance with good manufacturing practice (GMP), the Medical Devices Directive 93/42/EEC and local regulatory guidelines.

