7.2.5 Doses and treatment regimens

Each patient will self-administer a total of 6 doses of Gedea Pessary in the study. The pessary is slow-release formulated, administering 150 mg GDL and 184 mg NaG, over 24 hours.

The pessary will be self-administered vaginally by the patient at night, before going to bed. Instructions for use will be distributed at the first visit, advising patients on how to use the product together with the applicator. The patients will also be trained by site personnel in how to use the product, no previous experience of use is needed.

Briefly, patients will be instructed to wash their hands and vaginal area prior to use; place a tablet into the applicator and insert as far into the vagina as is comfortable (without forcing), or until half of the applicator is inside; discard the applicator after use; not use tampons or other vaginal products while using this product.

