7.2.2 Per Protocol Analysis Set

The per protocol analysis set (PPAS) is defined as the subset of subjects in the full analysis set for whom no protocol deviation judged as having an impact on the primary efficacy analysis was reported or identified.

Statistical Analysis Plan

Study ID: CL4

The decision as to which protocol deviations should be considered as reason for exclusion from the per protocol analysis set should be made at the clean file meeting and documented in the clean file report.

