7.8 Compliance

Compliance will be calculated as specified in Section 8.3. Compliance will be summarised for the full analysis set.

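### SAP 8.3: the kit-derived compliance formula subtracts single pessaries from whole kits, so one lost or unused pessary gives 0% instead of 83.3%, and two give -100% instead of 66.7%

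*SAP*

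**What the plan says.** SAP section 8.3 defines two compliance percentages. The patient-reported one is 100 times the number of treatment days (Day 0 to Day 5) with a yes in the app, divided by 6. The kit-derived one is 100 times "6 \times (\text{number of pessary kit returned} - \text{number of pessaries lost} - \text{number of returned unused pessaries})$ to the clinic divided by 6". On kits that are not returned the section adds: "Note that this definition implies non-compliance in case of failure to bring back kits to the clinic". The two are then combined: "Total study compliance will subsequently be derived as the maximum of patient reported compliance and pessary kit compliance".

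The protocol fixes the units. In section 7.2.2 the products are "packed in blister packs containing 6 pessaries packed together with 6 pessary applicators in a cardboard box", and section 7.2.5 states: "Each patient will self-administer a total of 6 doses of Gedea Pessary in the study". One kit is therefore one woman's full course.

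On use of the variable, SAP section 7.8 says: "Compliance will be summarised for the full analysis set". SAP section 7.2.2 gives no compliance cut-off for the per protocol set and leaves the choice of excluding deviations to the clean file meeting.

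**The concern.** The bracket mixes units: it takes counts of single pessaries away from a count of kits, and only then multiplies by 6. The 6 has a purpose only if it converts kits into pessaries, which means multiplying the kit count alone. As printed it is cancelled by the divisor and does nothing.

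With one kit returned, the kit-derived value can then only be 100%, 0% or negative. It cannot take any value from 16.7% to 83.3%, although partial use is exactly what a kit count should measure.

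What is at stake is a reported descriptive figure. A programmer who follows the text produces impossible percentages; one who silently corrects it departs from the signed SAP. Exposure also matters when this trial is read: protocol section 5.2 links the low cure rate in the earlier VVC study partly to pessaries that fell out or did not dissolve.

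**Working it through.** **Inputs.** Pessaries per kit: 6 (protocol 7.2.2). Planned doses per woman: 6 (protocol 7.2.5). Formulas and maximum rule: SAP 8.3. Planned number of women: 26. The documents give no numerical compliance result, so there is no figure of the plan's own to reproduce first.

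**Notation.** k = kits returned; m = pessaries lost + unused pessaries returned; y = diary yes-days.

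- As printed: 100 × 6 × (k − m) / 6 = 100 × (k − m).
- With the 6 on the kit count only: 100 × (6k − m) / 6.

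**Step 1: kit-derived value, one kit returned (k = 1).**

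| m | As printed | Corrected |
|---|---|---|
| 0 | 100% | 100% |
| 1 | 0% | 83.3% |
| 2 | −100% | 66.7% |
| 3 | −200% | 50.0% |
| 4 | −300% | 33.3% |
| 5 | −400% | 16.7% |
| 6 | −500% | 0% |

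**Step 2: could a kit mean a single pessary?** No. Six returned with none lost or unused would give 100 × 6 × 6 / 6 = 600%.

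**Step 3: total compliance.** The total is max(100y/6, kit value). With k = 1, the printed and corrected totals differ only if m ≥ 1 and y < 6 − m. Over y = 0 to 6 and m = 0 to 6 there are 7 × 7 = 49 combinations. Those that differ number 5 (m = 1) + 4 (m = 2) + 3 (m = 3) + 2 (m = 4) + 1 (m = 5) = 15. All 15 are too low as printed and none is too high. The shortfall runs from 16.7 points (for example m = 1, y = 4) to 83.3 points (m = 1, y = 0).

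- y = 4, m = 1: printed max(66.7, 0) = 66.7%; corrected max(66.7, 83.3) = 83.3%.
- y = 3, m = 1: printed max(50, 0) = 50%; corrected max(50, 83.3) = 83.3%.

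**Step 4: mean of the kit-derived value, if it is tabulated separately for 26 women.** Compared with full compliance, a woman with m = 1 lowers the mean by 100/26 = 3.85 points as printed, against (100/6)/26 = 0.64 corrected. With m = 2 the figures are 200/26 = 7.69 and (200/6)/26 = 1.28.

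**Step 5: kit not returned (k = 0).** With m = 0 both forms give 0%, as the SAP intends. With m = 1 the printed form gives −100% and the corrected form 100 × (0 − 1)/6 = −16.7%. Moving the bracket is therefore not enough; a floor at 0 is also needed.

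**The case against.** The strongest case is that the effect is narrow. The maximum rule gives the correct total whenever the diary is at least as high as the true kit count, and whenever nothing is lost or unused. A woman who skips a dose and says so gets the right total. Daily app reminders work against diary gaps. Protocol section 7.6 relies on the app question, plus vaginal pH for duration in vivo, and rules out further compliance measures, so the kit count is a supplement added by the SAP. Nothing inferential depends on it, and a value of −100% would be conspicuous in programming.

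Most of this stands as a limit on reach. It does not repair the formula. The patient-reported measure divides by a fixed 6, so an unanswered day counts as a missed dose. The kit count could correct that, but as printed it cannot do so once any pessary is lost or unused.

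Two further cautions are fair. The 15 of 49 is a count of possible combinations, some of them improbable, and not an expected frequency. Also, the formula was read here from a converted PDF in which the words *to the clinic* fall outside the closing bracket, so the bracket should be checked against the signed SAP. Nothing in the documents shows that the conversion moved it.

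**Conclusion.** The concern holds. As printed, the rule gives wrong and sometimes impossible kit-derived values: 0% for 83.3%, and −100% for 66.7%. It understates total compliance by 16.7 to 83.3 points when at least one pessary is lost or unused and the diary records fewer applications than the kit shows.

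The conclusion rests on two assumptions: one kit per woman, as the protocol plans, and an intended formula in which 6 converts kits to pessaries. The SAP does not state that intention, but no other reading examined fits 6 pessaries per box and a 0–100% scale for a woman who returns her kit.

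How many women would be affected cannot be known from the documents. The primary analysis is untouched; per protocol membership would be touched only if the clean file meeting uses this variable. The correction should be made: the error is clear, even though its reach is small.

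**What to change.** In SAP section 8.3, define kit-derived compliance as 100 × (6 × kits returned − pessaries lost − unused pessaries returned) / 6, bounded at 0–100%. Keep the maximum rule. Check the bracket in the signed SAP and confirm that the program follows the corrected text.

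The cost is one line of SAP text and a code check. With one kit per woman, the change can only raise total compliance or leave it as it is.

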7.6 Treatment compliance

Patients will be asked about investigational product administration via the mobile application on each treatment day (Day 0 to Day 5).

Vaginal pH assessments on Days 0 and 7 will be used as a measure of investigational product *in vivo* duration. If the vaginal pH on Day 7 is lower than the pH on Day 0, that would indicate appropriate release duration. It will be measured by site personnel on Day 0 and Day 7.

No other measurements of treatment compliance will be made.

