6.5.1 Vaginal candidiasis symptoms and pessary administration

The following information will be collected in the ePRO system.

Pessary administration:

At Days 0 to 5, the patient should confirm that they have administered the pessary:

Question on treatment days:

Have you applied the pessary?

- Yes
- No

If no, please provide reason: (free text).

Scoring of vulvovaginal candidiasis symptoms:

The vulvovaginal candidiasis (VVC) symptoms will be rated by all patients on Days 0 to 6, Day 11 and Day 25.

The VVC symptoms will be rated according to 0-3 scale, as shown below.

	0 = none (absent)	1 = mild (slight)	2 = moderate (definitely present)	3 = severe (marked, intense)
Itching				
Burning				
Irritation				

Statistical Analysis Plan

Study ID: CL4

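### When app and kit compliance conflict, SAP 8.3 always reports the higher figure, even where pessaries returned unused show that a dose cannot have been taken

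*SAP*

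**What the plan says.** Protocol 7.2.5 fixes the denominator: "Each patient will self-administer a total of 6 doses of Gedea Pessary in the study". Protocol 7.6 names two compliance sources, the app question on each treatment day and vaginal pH on Days 0 and 7, and closes with "No other measurements of treatment compliance will be made". Protocol 12.3 says compliance will be described and refers back to 7.6.

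The SAP goes further. Section 7.8 states "Compliance will be calculated as specified in Section 8.3" and places the summary in the FAS. Section 8.3 defines two measures:

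- **App measure.** 100 times "the number of ordinary study days (0 to 5) the patient responded yes to the question" on applying the pessary, divided by 6. SAP 6.5.1 describes the question: "At Days 0 to 5, the patient should confirm that they have administered the pessary". The answer is Yes or No, with a free-text reason for a No.
- **Kit measure.** The formula introduced by "Pessary kit derived compliance will be calculated as" starts from the kit returned and subtracts pessaries lost and pessaries returned unused. The SAP adds: "Note that this definition implies non-compliance in case of failure to bring back kits to the clinic".

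They are then combined: "Total study compliance will subsequently be derived as the maximum of patient reported compliance and pessary kit compliance". Section 8.3 gives no separate rule for sources that contradict each other, and it does not say that discordant patients will be counted or listed. SAP 7.10 lists five changes to the planned analysis; compliance is not one of them.

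**The concern.** The maximum has a sensible purpose. An unanswered app day lowers the app measure and a forgotten kit sets the kit measure to zero, so taking the better source rescues women whose records are merely incomplete. But the rule does not separate 'no data' from 'evidence that a dose was not taken'. A pessary that comes back in its blister cannot have been used, and a full set of app confirmations cancels that fact.

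Dosing is at home and unobserved. The 54% cure assumption in Protocol 12.6 rests on the new formulation overcoming the retention and dissolution problems of the earlier product. If the cure rate disappoints, the reader will want to know whether the product failed or was under-used. A compliance figure that settles every conflict upward is a poor guide to that.

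**Working it through.** The documents give no compliance figure to reproduce, so I applied the SAP 8.3 definitions case by case.

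**Inputs.** Six planned doses (Protocol 7.2.5); one kit of six pessaries (Protocol 7.2.2); app, kit and total rules (SAP 8.3).

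**Formulas.**
- App = 100 × (Yes days)/6.
- Kit, as apparently intended = 100 × (6 × kits returned − lost − unused)/6, which is 0 if the kit is not returned.
- Total = max(App, Kit).
- Physical ceiling when the kit is returned = 100 × (6 − unused − lost)/6.

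| Case | App % | Kit % | Total % | True % |
|---|---|---|---|---|
| 6 Yes; 1 returned unused | 100 | 83.3 | 100 | at most 83.3 |
| 6 Yes; 2 returned unused | 100 | 66.7 | 100 | at most 66.7 |
| 6 Yes; 3 returned unused | 100 | 50 | 100 | at most 50 |
| 4 Yes, 2 No; 2 returned unused | 66.7 | 66.7 | 66.7 | at most 66.7 |
| 4 Yes, 2 No; kit back, none unused or lost | 66.7 | 100 | 100 | not settled by the data |
| All 6 taken; 4 Yes, 2 unanswered; kit back, none unused or lost | 66.7 | 100 | 100 | 100 |
| All 6 taken; 4 Yes, 2 unanswered; no kit | 66.7 | 0 | 66.7 | 100 |
| All 6 taken; no app entries; no kit | 0 | 0 | 0 | 100 |

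The first three rows are the defect. The fourth shows that agreeing sources give a correct total. The sixth shows the rule doing its intended job. The last two show understatement.

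**Size.** One unused: 100 − 83.3 = 16.7 points. Two unused: 100 − 66.7 = 33.3 points. If all 26 planned women are in the FAS, one such woman moves the mean by 16.7/26 = 0.6 or 33.3/26 = 1.3 points.

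**Bracket in the kit formula.** As printed, the factor 6 multiplies the whole bracket, so one unused pessary gives 100 × 6 × (1 − 0 − 1)/6 = 0% and two give −100%. The bracket looks misplaced and should be checked, but no total in the table changes under the printed form.

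**Net direction.** This depends on error rates that the documents do not give. An illustration with assumed rates (200,000 simulated women per scenario, intended kit formula, 90% of doses truly taken, 10% of app entries missing, 20% of kits not returned):

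| Further assumption | Mean total % (true 90.0) | Overstated | Understated |
|---|---|---|---|
| No false reports | 88.2 | none | 8.6% |
| 30% of missed doses reported as Yes | 90.2 | 9.6% | 7.6% |
| The same, and 30% of unused pessaries not returned | 92.0 | 20.0% | 7.8% |

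**The case against.** Four points can be made for the plan.

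**The rule does not only inflate.** A reader might infer that adherence can only be overstated. The documents do not support that: both components fall when data are missing, and the last two rows of the case table show totals of 66.7% and 0% for women who took every dose. This stands, and it limits the point to conflicts between sources.

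**An app 'No' is weaker evidence than an unused pessary.** Dosing is at bedtime (Protocol 5.4.2), and SAP 6.5 keeps the first non-missing entry of a study day. A 'No' entered early in the evening therefore survives a later 'Yes'. The app measure counts only Days 0 to 5, so a dose taken late on Day 6 is missed as well. In both situations an empty kit is the better evidence and the maximum is right. This also stands, so a 'No' should not automatically remove a dose.

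**The consequence is modest.** Compliance is a descriptive FAS summary and does not enter the primary endpoint or its test. A reader might infer that under-dosed women will remain in the per-protocol result. SAP 7.2.2 sets no compliance threshold and does not mention total compliance; exclusions are decided at the clean file meeting. The inference is possible but not established. Table layouts are left to a Data Display Plan, so both components may yet be shown.

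**The departure from the Protocol is housekeeping.** Package return is already a Protocol procedure (5.4.3, 7.3), and SAP 2 allows changes that do not touch principal features to be recorded in the SAP alone. Section 8.3 does record this one. Even so, 7.10 is where a reader looks for changes, and Protocol 7.6 rules out further compliance measures.

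None of this answers the first three rows of the case table, where the reported total is physically impossible.

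**Conclusion.** The point holds for conflicts between the sources. With six app confirmations and 1 or 2 pessaries returned unused, SAP 8.3 reports 100% where at most 83.3% or 66.7% was possible. This assumes one six-pessary kit per woman, correct counts of returned pessaries and the kit formula as apparently intended; the 100% total is the same under the printed form.

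Three limits apply. Total compliance can also be understated, so no overall direction of bias can be claimed. The number of discordant women cannot be predicted from the documents. The effect is confined to the descriptive FAS compliance summary unless the clean file meeting uses that figure when it settles the per-protocol set. The kit measure's absence from SAP 7.10 is a secondary documentation point.

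It is worth correcting because the rule as stated yields a wrong figure and the data for a better one are already collected.

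**What to change.** Replace the maximum in SAP 8.3 with these rules:

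1. **Kit returned:** cap total compliance at 100 × (6 − unused returned − lost)/6. Lost pessaries are subtracted because the SAP's own formula does so.
2. **Kit not returned:** use the app measure alone.
3. **Unanswered app days with a returned kit:** fill them from the kit count.
4. **App 'No' with a kit showing no unused or lost pessaries:** flag the patient as discordant and review her before database lock, with no automatic resolution in either direction.

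Taking the minimum of the two measures, or subtracting both app 'No' answers and unused pessaries, is not a safe substitute. Returned pessaries carry no date, so one 'No' and one unused pessary may be the same dose (5/6) or two doses (4/6).

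Report both component measures and the number of discordant patients. Correct the bracket in the kit formula if it stands as printed. List the kit measure and the combination rule in SAP 7.10 as a change from Protocol 7.6.

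The cost is one SAP paragraph, a small programming change and a short pre-lock review, with no new data. Reported compliance may be slightly lower. Women with missing app entries and no kit will still be understated, so the text should say so.
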